We propose concurrently targeting four specific areas to improve the lives of women that have suffered from fistula including health education, physical rehabilitation, psychosocial therapy, and economic empowerment. Informed by theoretical frameworks adopted from the interdisciplinary fields of health behavior, women's empowerment, and implementation science and the developing evidence base previously discussed, addressing each of these areas will assist women in overcoming the mental and physical disabilities that they may have suffered as a result of the fistula (physical rehabilitation and psychological therapy), ensure they are appropriately educated about fistula and reproductive health for optimizing recovery and enhancing post-repair health (health education) and address their economic needs to improve quality of life and prevent fistula recurrence in subsequent delivery by achieving the status and financial standing to access timely obstetric care (economic empowerment). In addition, certain components of our anticipated intervention will be directly targeted to women's partners or close family members, who are important sources of social support and critical links between afflicted women and their communities. This will be the first rigorously designed and evaluated multi-component intervention to address all these theoretically important supports for female genital fistula reintegration to our knowledge.

Figure 1. Conceptual Framework Informing Intervention Needs of Women with Genital Fistula

APPROACH

OVERVIEW OF STUDY DESIGN

Given the pilot nature of the current project and our primary objective to understand intervention feasibility and acceptability outcomes, we propose a quasi-experimental design for the current study. The study is being done to inform the subsequent development of a cluster-randomized controlled trial to estimate impact on effectiveness; however, no randomization will be undertaken at this stage of the research, and all women enrolled in the study will participate in the intervention. Assessment of preliminary effectiveness (Aim 3) in the current pilot study is exploratory, and will include change over time from pre-surgery as well as comparison with existing data from similar women that was collected within the context of a different research study.

STUDY SETTING

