Our research program seeks to improve physical and psychosocial outcomes of women undergoing surgery for female genital fistula in Uganda. The data collection activities for the pilot test of the intervention will be based at two hospitals in Kampala, Uganda: Mulago Specialized Women and Neonatal Hospital and Kawempe National Referral Hospital, as fistula repair surgeries are conducted at both of these locations by the same team. These facilities were selected based on volume of fistula repair and prior clinical and research collaboration. They provide fistula repair as an ongoing urogynecological service, supplemented by several annual fistula repair camps. Surgeons are International Federation of Gynecologists and Obstetricians (FIGO) certified fistula surgical trainers who routinely supervise trainees country-wide. From 2010 through 2015, an average of 190 women per year underwent genital fistula surgery at Mulago Hospital.⁴⁹

In this setting, the current standard of care for women accessing fistula surgery includes some unstructured health education and counseling on post-repair behaviors, and women are instructed on kegel exercises for pelvic floor strengthening. Women with significant needs are referred. However, these adjunct services are not offered as a structured program and referral is only made for the most severe cases, leaving women who might benefit from some psychological and physiotherapy services without.

STUDY PARTICIPANTS

Study participants will include 30 women who receive surgical care for female genital fistula at Mulago and Kawempe Hospitals in Kampala, Uganda. Women are referred to these services from providers at Mulago/Kawempe, nearby clinics or hospitals, or learn about the services from friends, relatives, and radio advertisements. Women will be considered eligible for participation after undergoing fistula surgery, if they are above age 18 or considered emancipated minors under Ugandan law, and if they are able to provide consent for the study. Up to 15 of the intervention recipients will be invited for subsequent in-depth interview for a more nuanced understanding of their experience participating in the intervention and its impact; they will be purposively selected with variability in the range of outcomes observed in the quantitative data collection: reintegration score, depression/anxiety, and economic status. This sample size has been selected for feasibility.

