Acceptability assessment (Aim 2) will incorporate interviews with up to 10 key stakeholders including facility staff implementing the intervention (n=3-5), providers working in fistula care at the facility, who will have spoken with women receiving the intervention but who have not directly delivered the intervention, (n=2-4) and hospital administrators *who may have important insight on implementation of the intervention outside of a research context and its sustainability* (n=1-2). This sample size has been selected for feasibility.

One of our exploratory comparisons for preliminary effectiveness (Aim 3) will be among the same participants (pre-post); however, the other comparison will be with existing data collected during a longitudinal cohort study we conducted among 60 women undergoing fistula care at Mulago Hospital in 2015-2016 and followed for a 1-year period.^{11,14}

RECRUITMENT AND ENROLLMENT

Intervention recipients: Potential intervention recipients will be recruited for participation in the study at the fistula ward at Mulago/Kawempe. Given current and historical rates of women's presentation for fistula care, we plan to recruit all women who present for care who meet our eligibility criteria. Our research staff will identify which women meet the eligibility criteria of the study based on personal knowledge, review of surgical logbooks and through discussion with other fistula ward personnel. Women will be approached for recruitment when identified as eligible, potentially several days prior to surgery. Study staff will describe the study goals and procedures, ensuring women's understanding of the study procedures and risks, and ascertain women's interest in participating through the informed consent process. Women who are interested in participating will be requested to provide written confirmation of consent through signature or thumbprint (with witness).

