Key stakeholders: 10-15 key stakeholders, who are individuals known to the study investigator team, will be invited for in-depth interview through in-person, phone, or email. We will purposively select representation from a range of stakeholders including facility staff implementing the intervention (n=3-5), providers working in fistula care at the facility (n=2-4) and hospital administrators (n=1-2). Individuals who are interested will be scheduled for interview, and the qualitative interviewer will lead the individual through the informed consent process prior to starting the interview.

STUDY PROCEDURES

Immediately after study enrollment, women will be requested to complete an interviewer-administered baseline questionnaire including sociodemographic characteristics, assessment of physical and psychosocial health and reintegration status. Follow-up data collection will occur at hospital discharge, 6w, 3m, and 6m following surgery. Data collection at the 6-week time point will be conducted in-person as women come to the facility then for their clinical follow-up visits. Data collection at the 3 and 6 month study visits will be captured via mobile phone, which we have previously shown to be feasible and acceptable among this population,⁵⁰ to reduce participant burden. Data on fistula characteristics and procedures will be abstracted from participant medical records and collected from providers. In order to facilitate study communication and follow-up data collection, women who do not possess a personal phone will be provided with one by the study, and \$6 monthly airtime will be provided for the length of the study.

The multi-component intervention incorporates health education, psychosocial counseling, physical therapy, and economic empowerment across the 14-day period that women typically stay at the facility for fistula surgery and through their 6-week and 3-month follow-up visits. The content, rationale and general delivery structure of each component is described in Table 1 below, with our detailed intervention timeline presented in Figure 1.

Table 1. Specific Components of Post-Surgical Reintegration Intervention

Component	Content and rationale	General delivery structure

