size. However, for a feasibility study such as ours, we anticipate this will provide important information regarding optimal group size. Furthermore, in the event that women are the lone fistula patients, we will adapt the intervention content to an individualized setting. Two individual psychological counseling sessions will be delivered – the initial session pre-op and the final session prior to discharge. The health education and psychosocial counseling component of the intervention will occur within the fistula-repair hospital admission; however, the physiotherapy component will extend through the 6-week post-surgical visit, and the economic investment and associated informational session will be provided at the 6-week post-surgical visit.

Table 2. Intervention Timeline

Component Session No.	Pre-op 1 1	Pre-op 2 2	Surgery & Post-Op 1	Post-op 2 3	Post-op 3 4	Post-op 4 5	Post-op 5 6	Post-op 6 7	Post-op 7 8
HE	Admission and pre-op mgmt, 30m	Pre-op mgmt, 25m	Surgery + Post-op Day 1: No intervention sessions	Post-op mgmt, 30m		Fistula causes, 30m		Health and social consequences of fistula, 20m	
PC		Intro to counseling, 40m individual		Repro system anatomy & function, 30m		Common fistula myths/misconcept 30m		Fistula prevention, 40m	
PT		Intro to PT, 20m Mobility and pelvic floor assessment, 15m Daily: Breathing & functional mobility exercises, 15m			Explore fistula experience, 60m		Cognitive reframing of fistula experience, 30m		Identifying thoughts/emotions, 40m Practice reframing problematic thoughts, 20m
Total time	75m + 40m ind	75m + 40m ind		0m	75m	75m	75m	75m	75m
Component Session No.	Post-op 8 9	Post-op 9 10	Post-op 10 11	Post-op 11 12	Post-op 12 13	Post-op 13 14	Post-op 14 15	Other Sessions TBD	
HE	Sexual/RH after fistula, 30m Family planning, 30m		Obstetric care, 30m Nutrition, 30m		Post-discharge management, 30m Recap, 30m	Recap, 30m	Recap, 30m	Health education for family/caretaker, 60m	
PC		Coping skills, 40m Social support and relationships, 20m		Planning for future, 60m		Pre-discharge review, 60m individual		Building social support with family/caretaker, 60m	
PT		Daily: Breathing & functional mobility exercises, 15m			Daily: Breathing & functional mobility exercises, 10m Individual assessment, treatment plan, 40m		Daily: Breathing & functional mobility exercises, 15m	Individual assessment, treatment plan, 40m @ 6w	
Total time	75m	75m	75m	75m	75m + 40m individual	45m + 40m ind	45m + 40m ind		

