Quantitative data. Data from surveys will be entered into a password-protected database. Confidentiality will be protected by secure data handling. Data quality practices will include range and logical checks built into data entry, double entry, and error checks. We will examine overall status at each time point for each variable, investigate patterns and types of missing data and non-response, and inspect distributions of mediating and outcome variables to identify outlying or unusual values and assess distributional characteristics. Data analysis: We will describe respondent characteristics and primary outcomes (Aims 1&2 - acceptability and feasibility; section a in Table 2) using frequency tables and descriptive statistics (e.g. means, standard deviations, medians, inter-quartile ranges, and proportions). Preliminary effectiveness (Aim 3) will be conducted by bivariate comparisons of pre vs. post assessments (within our main sample) of reintegration score (primary), quality of life and depression (secondary) and comparison between our external control group using similar data from the same time since surgery using the appropriate distributional tests (paired sample t-test and Stuart-Maxwell tests for pre-post comparison, and two sample t-test and chi-square test for external comparison).

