Qualitative data will be recorded and transcribed, and translated into English (if necessary). Thematic analysis will involve a two-stage process⁹⁶. First, data will be coded and classified with transcript review for potential conceptual categories, using the guideline questions as initial categories. Two types of codes will be employed. Deductive codes that represent expected influences on the outcomes will be applied to the data: these will be taken from our qualitative guide informed by Proctor's framework.⁶⁴ Inductive codes emerging organically from the data will be applied: these codes will represent themes unexpected by the researchers and will be identified by recurrence rate and on similarities and differences across the texts. A codebook will include a detailed description of each code, inclusion and exclusion criteria, and examples of the code in use. Coded data will be analyzed to describe the different dimensions and commonalities of each theme, their distribution across participant type and the patterns and linkages between themes. This will allow us to build concepts grounded in the data to explain phenomena. Comparisons will be made with the data to detect divergent views among the participants and to contrast observations that relate to variables within the sample population.

TIMELINE

The planned study timeline is detailed below. We hope to begin participant recruitment in Dec 2020 and anticipate reaching our target sample size within four months. Baseline data collection will occur at recruitment, thus will span this full time period. Data collection for 6w, 3m, and 6m time points are detailed below. Quantitative analysis will occur throughout data collection, with analysis finalized in September 2021. Qualitative data collection will occur from Feb – Jul 2021, with concurrent analysis. Integration of quantitative and qualitative analyses will be done in Sept – Oct 2021. We plan to develop our research proposal for a larger trial to test effectiveness of the intervention from Aug – Oct 2021, submitting to the U.S. National Institutes of Health in October 2021.

Table 3. Study timeline, October 2020 – October 2021

	2020					2021							
	Oct	Nov	Dec	Jan	Feb	Mar	Apr	May	Jun	Jul	Aug	Sep	Oct
IRB review	X	X	X	X	X								
Staff training on intervention protocol			X	X	X								
Participant recruitment					X	X	X						
Quantitative data collection													
Data collection, baseline					X	X	X						
Data collection, 6w						X	X	X					

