Appendix 1A. Overview of Reintegration Intervention: Health Education Sessions

Session	Objective	Length	Timing ^a	Delivery ¹
1. Admission and Preoperative Management: Preparing for Upcoming Surgery and Recovery (Part 1)	
 Introduce patients to fistula Introduce patients to care providers Provide a comprehensive overview of procedure, risks, and outcomes Address any patient concerns and questions about procedure and recovery 	30m	Pre-op Day 1	Group
2. Admission and Preoperative Management: Preparing for Upcoming Surgery and Recovery (Part 2)	
 Familiarize patients to the patient ward and the surgical theatre Discuss preoperative preparations Discuss postoperative management Address any patient concerns and questions about procedure and recovery 	30m	Pre-op Day 2	Group
Surgery Day 0				
Post-op Day 1				
3. Overview of Postoperative Management	
 To discuss outcomes of surgery To discuss postoperative care management at the facility Address any patient concerns and questions 	30m	Day 2 (post-op)	Group
4. Reproductive system anatomy and function	
 Familiarize participants with the female reproductive system and female pelvis, anatomy and functions 	30m	Day 2 (post-op)	Group
5. Development of Fistula	
 Identify the causes of obstetric fistula 	30m	Day 4 (post-op)	Group
6. Common Myths and Misconceptions about Fistula	
 To dispel any common rumors and myths about obstetric fistula To explaining how these may hamper women's ability to prevent fistula and to access treatment 	30m	Day 4 (post-op)	Group
7. Health and Social Consequences of Fistula	
 To identify and discuss the health consequences of fistula To identify and discuss the social consequences of fistula 	20m	Day 6 (post-op)	Group
8. Fistula Prevention	
 To discuss ways to prevent obstetric fistula after repair To introduce birth spacing 	40m	Day 6 (post-op)	Group

¹ Where group is indicated but women are in undergoing fistula repair without other fistula patients concurrently on the ward, they will receive a modified version of the activity appropriate for delivery to the individual.

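### The eligibility sentence places entry after surgery, against pre-operative recruitment, the pre-operative sessions and Aim 3's pre-surgery reference, so baseline timing is not fixed

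*Combined protocol and SAP*

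**What the plan says.** Entry. The only eligibility statement, in Study Participants, reads: "Women will be considered eligible for participation after undergoing fistula surgery". It adds conditions on age and capacity to consent. Recruitment and Enrollment says: "Women will be approached for recruitment when identified as eligible, potentially several days prior to surgery". The Project Summary places recruitment at the time of repair.

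Baseline. Study Procedures says: "Immediately after study enrollment, women will be requested to complete an interviewer-administered baseline questionnaire". The Timeline section says: "Baseline data collection will occur at recruitment". Neither sentence refers to the date of surgery.

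Use of the baseline. Overview of Study Design says that the Aim 3 assessment "will include change over time from pre-surgery". Specific Aims describes the same contrast as baseline to six months. Data Analysis Plans tests it with paired pre-versus-post methods on reintegration score (primary for Aim 3), quality of life and depression.

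Intervention. The text before the intervention timeline (Table 2) times the two individual counseling sessions as "the initial session pre-op and the final session prior to discharge". Appendices 1A to 1C place health education sessions 1 and 2, counseling session 1 and physiotherapy sessions 1 and 2 before surgery. None of these is marked optional.

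**The concern.** The eligibility and recruitment sentences cannot both be followed. If a woman becomes eligible once she has been operated on, nobody can be approached as eligible several days beforehand. Because the baseline follows enrollment, whichever sentence the staff apply also decides whether a woman's baseline falls before or after her repair.

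The two kinds of baseline start from different places. Change from a pre-surgery score to six months includes whatever the repair itself does. Change from a score taken on the ward afterwards starts once the repair has been done, and in the post-operative state. A mean over a mixture of the two estimates neither, and no text limits the paired test to women whose baseline preceded surgery.

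Late entry also removes the pre-operative part of the intervention, including the first mobility and pelvic floor assessment, which cannot be recovered later. Fidelity is a secondary implementation outcome, judged by whether delivery matched intent. Sessions that were impossible because of late entry would be hard to tell apart from sessions that were not delivered.

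**Working it through.** The plan gives no figure of its own to reproduce here. The sample size of 30 rests on feasibility, with no power or error rate. The check is therefore a comparison of texts, a count of minutes, and an expression for what cannot be quantified.

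**1. Texts side by side**

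| Place | Timing implied |
|---|---|
| Study Participants | eligible after surgery |
| Recruitment and Enrollment | approach possibly days before surgery |
| Project Summary | recruitment at the time of repair |
| Study Procedures; Timeline | baseline at enrollment or recruitment, surgery not mentioned |
| Overview of Study Design | change measured from before surgery |
| Text before intervention timeline; Appendices 1A–1C | sessions before surgery in three components |

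The last two rows need pre-surgery entry. The first row rules it out if taken literally, the second permits it without requiring it, and the third and fourth do not settle it.

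**2. Scheduled non-optional inpatient minutes (Appendices 1A–1C)**

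The optional family sessions and the 6-week and 3-month follow-up are left out.

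- Health education, sessions 1–14: 12 × 30 + 20 + 40 = 420. Pre-operative: 30 + 30 = 60, or 60/420 = 14.3%.
- Counseling, sessions 1–8: 40 + 60 + 60 + 60 + 40 + 20 + 60 + 60 = 400. Pre-operative: 40, or 40/400 = 10.0%.
- Physiotherapy: 35 + 2 × 15 + 12 × 15 + 15 + 40 = 300. Pre-operative: 35 + 2 × 15 = 65, or 65/300 = 21.7%.
- Total: 420 + 400 + 300 = 1,120. Pre-operative: 60 + 40 + 65 = 165. Share: 165/1,120 = 14.7%.

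This counts physiotherapy session 2 on both pre-operative days, as Appendix 1C lists it. Counted once, the share is 150/1,105 = 13.6%.

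**3. Effect on the mean paired change**

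Let m of the 30 women have a post-surgery baseline, and let d be the average amount by which a post-surgery baseline score differs from the score the same women would have given before surgery. With complete follow-up, the mean change moves by d × m/30 in absolute size. The documents allow any m from 0 (all approached before surgery) to 30 (eligibility sentence applied literally), and they give neither the size nor the sign of d. The shift therefore cannot be quantified.

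**The case against.** The strongest reply is that the eligibility sentence is a drafting slip and the intent is plain. Recruitment before surgery is expressly allowed, the intervention timeline has two pre-operative days, three appendices schedule pre-operative sessions, and Aim 3 names pre-surgery as its reference. This largely stands. A reader might infer from the eligibility sentence that every woman will have a post-surgery baseline and no pre-operative sessions. The documents do not support that: the sentence does not say that women are eligible only after surgery, and the recruitment text is also a written rule. But that text says pre-surgery approach is possible, not required, so even the favorable reading leaves room for a mix.

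Figure 2 shows the data collection timeline and cannot be read here. It may place baseline before surgery. The point is therefore limited to the readable text.

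The consequence is also limited. Aim 3 is labeled exploratory, the primary outcomes are feasibility and acceptability, and these are analyzed descriptively. The six-month external comparison does not use the baseline. All of this stands and holds the point to a moderate level.

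Finally, pre-operative sessions missed through late identification are a genuine feasibility result. That is right: they should be reported with their cause, not scored as not applicable.

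**Conclusion.** The contradiction is real and should be corrected. The one eligibility statement is incompatible with the recruitment text, the pre-operative sessions and the pre-surgery reference for Aim 3, and no readable text fixes the baseline before surgery. A mixture of baselines is possible, and it would blur the exploratory pre-post comparison of reintegration, quality of life and depression.

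The one size that can be given is for a woman who enters after surgery: she would miss 165 of 1,120 minutes (14.7%), on the Appendix 1 session lengths. Whether any woman will enter that late is not known. A reader might go further and infer that the pre-post estimate is biased by a certain amount or in a certain direction. The documents support neither, since they give no information on d or m.

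**What to change.** - **Eligibility.** Make women eligible when they are scheduled or admitted for fistula surgery, and require consent and the baseline questionnaire before surgery.
- **Women first identified after surgery.** Choose one rule in advance. Either do not enroll them, or enroll them for Aims 1 and 2 only, leave them out of the pre-post test, and report their missed pre-operative sessions separately as due to late enrollment.
- **Baseline timing.** Derive it relative to surgery for each woman. Follow-up is already timed from surgery, procedure data are abstracted from medical records, and dates are among the data collected, so a new field is probably not needed.

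The change costs an eligibility sentence and an analysis sentence. The first rule for late-identified women may slow recruitment slightly, and the second takes the paired sample below 30. Under pre-surgery enrollment, some enrolled women may have their surgery cancelled, and the plan should say how they are counted.

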The current proposal seeks to address the gap in evidence-based practice for reintegration following female genital fistula surgery through pilot testing of a multi-component intervention compiled by our experienced team of clinicians and researchers. Building on the existing evidence around reintegration programming, it will comprise four components: health education, physical rehabilitation, psychosocial counseling, and economic empowerment. The pilot intervention is strengthened by our prior work among women with fistula, including our expertise in assessment of recovery from female genital fistula surgery.^{11,13-15} Our study objective is to understand feasibility and acceptability of the intervention in preparation for a subsequent effectiveness trial. Using a quasi-experimental design, we will pilot the intervention protocol among 30 women undergoing fistula surgery at Mulago/Kawempe Hospital, assessing feasibility and acceptability using a convergent mixed-methods approach, capturing data from up to 15 intervention participants and up to 10 key stakeholders (e.g., intervention moderators, providers, administrators). Our specific aims are as follows:

SPECIFIC AIMs

Aim 1. To assess the feasibility of the pilot reintegration intervention. The intervention protocol will be piloted with 30 women seeking fistula care at Mulago/Kawempe Hospital in order to understand feasibility of the intervention and intervention assessment activities. Feasibility outcomes will include process assessment of recruitment and retention, data collection, outcome measures, study procedures, study resources and study management.

Aim 2. To assess the acceptability of the pilot reintegration intervention. Within the pilot intervention study, we will assess the acceptability of the intervention to patients, intervention implementers, providers, and hospital administration. Acceptability domains to be assessed include affective attitude, burden, perceived effectiveness, ethicality, intervention coherence, opportunity costs and self-efficacy.

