EE: Economic empowerment component will be distributed at the 6-week visit

HE: Health Education, PC: Psychosocial Counseling; PT: Physiotherapy; EE: Economic Empowerment

Data collection

[figure not shown]
The data collection timeline is displayed in Figure 2. As previously mentioned, baseline data and 6-week data will be collected in person, and subsequent interviews (3 and 6 months) will be administered over the phone. To facilitate data collection, participants will be provided with a basic telephone (adequate for texting and calls) if needed which they will keep even if they choose to stop participation in the study, and airtime sufficient for study participation and some discretionary use. Additional airtime will be provided monthly.

We will collect the longitudinal data via surveys on intervention feasibility and acceptability, reintegration, mental health (i.e., quality of life, depression, traumatic stress, anxiety), physical health (incontinence), social support, stigma, and income measures (i.e., food security, income) through 6 months following surgery. Respondents will be re-interviewed about demographic questions that may change over time (i.e., partnership, labor force participation) to detect reverse causation. We do not anticipate issues around retention given the high retention rates seen in our own⁵⁰ and other fistula studies.⁶³

We will conduct in-depth interviews (3-6m after surgery) among approximately 10-15 participants using an open-ended semi-structured guide to understand women's experiences with the intervention, and to explore acceptability and effectiveness of each of the intervention components in a more nuanced and subjective manner. In-depth interview participants will be purposively selected for observed variability in outcomes observed during data collection, including reintegration score, depression/anxiety scores, economic status.

In-depth interviews with key stakeholders (intervention implementers, providers, and hospital administration) will be conducted within this same timeframe to understand their perspectives on intervention acceptability.

Figure 2. Data Collection Timeline

STUDY MEASURES

The intervention evaluation will use quantitative and qualitative methodologies, following Proctor's implementation outcome framework,^{64,65} including measures of acceptability, adoption, appropriateness, costs, feasibility, fidelity, penetration and sustainability.

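### Interviewees are chosen for spread in outcomes but not in attendance or satisfaction, so the acceptability interviews may by chance include no woman who attended little or was dissatisfied

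*Combined protocol and SAP*

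**What the plan says.** The Study Participants section gives the size of the pool ("Study participants will include 30 women who receive surgical care for female genital fistula") and of the interview sample ("Up to 15 of the intervention recipients will be invited for subsequent in-depth interview"). It states the selection rule: "they will be purposively selected with variability in the range of outcomes observed in the quantitative data collection: reintegration score, depression/anxiety, and economic status".

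The Data collection section repeats the rule in similar words: "In-depth interview participants will be purposively selected for observed variability in outcomes observed during data collection, including reintegration score, depression/anxiety scores, economic status". It gives the number and timing as "We will conduct in-depth interviews (3-6m after surgery) among approximately 10-15 participants", and the purpose as "to explore acceptability and effectiveness of each of the intervention components in a more nuanced and subjective manner".

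Acceptability and feasibility are the primary outcomes. Aim 2 sets out what acceptability covers: "Acceptability domains to be assessed include affective attitude, burden, perceived effectiveness, ethicality, intervention coherence, opportunity costs and self-efficacy". The measures table in the Study Measures section assesses acceptability through satisfaction, overall and for each component. The same section provides for process data on participation and engagement, and for longitudinal surveys of acceptability and experience. Neither statement of the selection rule mentions attendance, adherence, satisfaction or stopping.

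**The concern.** A purposive sample shows variation on the characteristics used to choose it. Here these are reintegration, depression/anxiety and economic status. Of the seven acceptability domains, only perceived effectiveness lies close to them. Burden, ethicality, coherence and opportunity costs are different matters.

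The selection variables may also largely reflect physical recovery. The protocol's introduction reports that, at twelve months, women with persistent symptoms scored 21.9 points lower on reintegration than women without. A woman who healed well but found the sessions a burden, and one who healed poorly but valued them, would be told apart on outcome. The rule would not identify either by her view of the programme.

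The pilot is meant to improve the intervention before a larger trial. A survey score can show that a woman was dissatisfied; the interviews are there to explain why. If no such woman is interviewed, that explanation is missing for a primary aim.

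**Working it through.** The plan gives no probability or expected rate on this point, and the number of interviews rests on feasibility. There is no figure to reproduce. The check has two parts.

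**1. What is collected against what is used for selection**

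| Variable | Collected? | Named as a selection criterion? |
|---|---|---|
| Reintegration score | Yes | Yes |
| Depression/anxiety | Yes | Yes |
| Economic status | Yes | Yes |
| Session participation and engagement | Yes (Study Measures) | No |
| Satisfaction, overall and by component | Yes (measures table) | No |
| Early stopping or missed follow-up | Yes (follow-up failures and completion rates are monitored, Data and Safety Monitoring) | No |

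**2. Illustrative chance that no such woman is interviewed**

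Inputs:
- N = 30 women (Study Participants).
- n = 10 or 15 interviews, the two ends of the range in the Data collection section.
- k = number of low attenders or dissatisfied women. The documents give no value; 2 to 5 is an assumption.
- Selection is taken as unrelated to attendance and satisfaction. This too is an assumption, since the plan selects purposively.

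Formula: P(none) = C(30 − k, n) / C(30, n).

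With n = 10:
- k = 2: (20 × 19) / (30 × 29) = 380 / 870 = 0.437
- k = 3: (20 × 19 × 18) / (30 × 29 × 28) = 6,840 / 24,360 = 0.281
- k = 4: 0.281 × 17/27 = 0.177
- k = 5: 0.177 × 16/26 = 0.109

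With n = 15:
- k = 2: (15 × 14) / (30 × 29) = 210 / 870 = 0.241
- k = 3: (15 × 14 × 13) / (30 × 29 × 28) = 2,730 / 24,360 = 0.112
- k = 4: 0.112 × 12/27 = 0.050
- k = 5: 0.050 × 11/26 = 0.021

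| k of 30 | 10 interviews | 15 interviews |
|---|---|---|
| 2 | 44% | 24% |
| 3 | 28% | 11% |
| 4 | 18% | 5% |
| 5 | 11% | 2% |

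The real chance could differ in either direction. If dissatisfaction goes with poor outcomes, sampling for outcome spread draws such women in and the chance falls. If dissatisfied women are also those lost before the interviews at 3-6 months, it rises.

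**The case against.** The case for leaving the rule alone has several parts.

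- **Outcome sampling has a stated reason.** The interviews also cover impact and effectiveness, and perceived effectiveness is itself an acceptability domain. Seeking spread brings in women with poor reintegration or high distress, some of whom may have felt the burden most. This stands, and it is why the outcome criteria should be kept.
- **The list may be open.** The Data collection section introduces the three outcomes with the word including. That leaves room for others, but it names none, and the Study Participants section lists only the three.
- **Other sources inform Aim 2.** A reader might infer that dissatisfied women drop out of the acceptability assessment altogether. The documents do not support that. Satisfaction and experience are surveyed and not only among interviewees, and implementers, providers and administrators are interviewed too.
- **Women who stop can often still be placed.** A reader might infer that, with interviews at 3-6 months, women who stop are almost sure to be excluded. That is too strong. The Study Procedures section collects data at discharge and 6 weeks as well, and the rule does not require 3- or 6-month data. Health education and counselling take place during the admission, so a woman who skipped sessions can still complete later surveys. Only women lost before any follow-up survey are really hard to place.
- **The percentages rest on assumed counts.** This also stands; they show scale and do not predict.

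What remains is that nothing in the rule ensures variation on acceptability, although the data to do so are collected.

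**Conclusion.** The point holds as a limited gap in the sampling rule. The interviews are meant to explore a primary outcome, but their sample is not spread on the variables closest to it. By chance they may include no low attender or dissatisfied woman. With 2 to 5 such women among 30, that chance runs from 44% to 11% with 10 interviews and from 24% to 2% with 15, on the two assumptions stated: the counts, and selection unrelated to attendance and satisfaction.

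The risk is confined to the interview evidence. A reader might also conclude that the interviews will be biased towards a favourable result. The documents do not show this: they do not say how the outcome measures relate to women's experience of the sessions, and outcome spread may bring in some critical voices. The gap is worth closing because closing it is cheap.

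**What to change.** In the Study Participants and Data collection sections, add three criteria to the existing outcome criteria: session attendance, satisfaction rating, and early stopping or missed follow-up where the woman agrees to be contacted. State that some of the 10-15 interviews will go to women with low attendance or low satisfaction, or who stopped. Use the same list in both sections.

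How many places to set aside is for the team to judge, and outcome variability can guide the rest. With even one place set aside, an identified woman of this kind is interviewed by design, provided she can be reached and agrees.

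The change is to wording only. It uses data already collected and the same number of interviews. The cost is slightly fewer places to illustrate variation in outcomes, and some effort to reach women who stopped.
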